6.2 Study Questionnaires

All subjects will undertake a number of study questionnaires at screening, baseline, and selected follow-up visits.

The Behavioural Questionnaire

The study staff will assist participants to complete this questionnaire. The behavioural survey will collect information on the following:

- Demographics
- HIV and drug treatment history
- Drug and alcohol usage
- Treatment acceptance and willingness (prior to treatment commencement only)
- Attitudes and behaviours associated with HCV reinfection
- Injecting risk behaviours (including information about injecting sharing partners and equipment sharing)

An abbreviated behavioural questionnaire (follow-up) will be administered at subsequent time points during the study.

Health Outcomes Survey (EQ-5D)

The EQ-5D health questionnaire provides a simple descriptive profile and a single index value for health status. This information can then be translated into a health utility, which can be used for cost-effectiveness analyses.

Adherence Survey

Adherence to elbasvir/grazoprevir will be assessed by a four-weekly structured self-report adherence questionnaire and four-weekly pill count.

6.3 Linkage of data (optional)

Participants are invited to consent to link their data collected during the DARLO-C study with routinely collected data from a range of population Health and Incarceration databases and registers.

The collection of participant names, date of birth, sex, and post code in DARLO-C is essential for accurate data linkage. Participant data will be linked to a variety of health variables including information on hepatitis C notifications, HIV/AIDS notifications, use of hepatitis services, use of prescription medication (including hepatitis C treatment), OST, incarceration, hospitalizations, emergency department use, cancer, and mortality through the New South Wales Centre for Health Record Linkage (www.cherel.org.au), and the Australian Institute of Health and Welfare (www.aihw.gov.au). Linkage will be both retrospective and prospective, with the time period covered dependent on the properties of the specific data set. Approval from the NSW Population and Health Services Research Ethics Committee, and all other required Human Research Ethics Committees will be sought prior to any data linkage being performed.

Participants are given the option to opt out of the health and incarceration data linkage component of this study on the Participant Consent Form. Participants not wishing to have their data used in the data linkage studies may still enroll in DARLO-C.

7. Recording and reporting Adverse Events (AEs)

7.1 Definitions of Adverse Events, Adverse Reactions and Serious Adverse Events

7.1.1 Definitions of Adverse Events, Adverse Reactions and Serious Adverse Events

The medications for this study are supplied via the PBS. Adverse events and adverse drug reactions will be reported to the Therapeutic Goods Administration as per standard practice for PBS prescribed medications. Only serious adverse events will be reported as detailed below.

7.1.2 Definition of Serious Adverse Events (Including Serious Adverse Drug Reactions)

The definition of a SAE is any untoward medical occurrence that at any dose:

- Results in death
- Is life-threatening

(Note: the term “life-threatening” in the definition of “serious” refers to an event/reaction in which the participant was at risk of death at the time of event/reaction; it does not refer to an event/reaction which hypothetically might have caused death if it were more severe)

- Requires in-patient hospitalisation or prolongation of existing hospitalisation
- Results in persistent or significant disability/incapacity
- Is a congenital anomaly/birth defect
- Results in a medically important event or reaction (includes infections from contaminated medicinal product/s). Other important medical events that may not result in death, not be life threatening, or not require hospitalization may be considered a serious adverse experience when, based upon appropriate medical judgment, the event may jeopardize the subject/patient and may require medical or surgical intervention to prevent one of the outcomes listed above. Examples of such medical events include allergic bronchospasm requiring intensive treatment in an emergency room or at home, blood dyscrasias or convulsions that did not require hospitalization, or development of drug dependency or drug abuse.
- Is an overdose of study medication (whether accidental or intentional)
- Cancer (that is not the condition under the study)*

All Serious Adverse Events, regardless of causal relationship to the investigational product, must be forwarded to **Merck Worldwide Product Safety** via fax ([contact]) within 2 working days of the investigator becoming aware of the event and no later than 3 calendar days.

Medical and scientific judgment should be exercised in deciding whether other situations should be considered serious e.g. important medical events that may not be immediately life-threatening or result in death or hospitalisation, but may jeopardise the participant or may require intervention to prevent one of the outcomes listed in the definition above.

Serious adverse events are collected from screening through to 4 weeks post end of treatment (SVR4).

7.2 Assessment of Serious Adverse Events

7.2.1 Assessment of Causality for Study Drugs and Procedures

The investigator or designee must assess each adverse event for the following:

Relationship

- Unlikely: An adverse event that is unlikely to be related to the use of the drug or procedures
- Possibly: An adverse event that might be related to the use of the drug or procedures
- Probably: An adverse event that is likely to be related to the use of the drug or procedures

7.2.2 Assessment of Severity

The investigator or designee must assess each adverse event for the following:

Severity

- Mild: Discomfort noticed but no disruption of normal daily activity
- Moderate: Discomfort sufficient to reduce or affect normal daily activity
- Severe: Incapacitating with inability to work or perform normal daily activity

Life threatening: Represents an immediate threat to life

7.3 Reporting Requirements

7.3.1 Adverse Events

An adverse event means any unfavourable and unintended change in the structure, function, or chemistry of the body temporally associated with any use of the Merck product whether or not considered related to the use of the product. Any worsening (i.e., any clinically significant adverse change in frequency and/or intensity) of a pre-existing condition which is temporally associated with the use of the product, is also an adverse experience.

Adverse events and adverse drug reactions will be reported to the Therapeutic Goods Administration as per standard practice for PBS prescribed medications.

7.3.2 Serious Adverse Events

All serious adverse events (SAEs) should be reported within TWO (2) WORKING DAYS of becoming aware of the event to the Kirby Institute and Merck by fax on the Serious Adverse Event Reporting Form. The appropriate Serious Event form should be used. Reports should be followed promptly by detailed, written follow-up reports when all information is not included in the initial report. Follow-up reports should be reported within TWO (2) WORKING DAYS also. The immediate and follow up reports should identify participants by unique code numbers assigned to study participants rather than personal identification. The investigator must also comply with all applicable ethical and regulatory requirement/s relating to the reporting of serious adverse events.

Any serious adverse event that is ongoing at the post-study follow-up visit must be followed until resolution or until the event stabilizes (for those events that will not resolve).

For deaths, the Principal Investigator will supply the sponsor and the IRB/IEC with any additional requested information (e.g. death certificate, autopsy reports and medical reports).

Merck (Attn: Worldwide Product Safety; [contact]) will be provided with copies of all serious adverse experiences regardless of causality to use of a Merck product within two working days. Additionally, any pregnancy occurring in association with use of a Merck Product will be reported (Attn: Worldwide Product Safety; [contact]).

A copy of all 15 Day Reports is submitted as required by local regulators by the investigator. This submission will be cross referenced according to local regulations to the Merck Investigational Compound Number (IND, CSA, etc.) at the time of submission. Additionally, a copy of these reports will be submitted to Merck (Attn: Worldwide Product Safety; [contact]) at the time of submission to local regulator.

SAE reports must be submitted to **BOTH the Kirby Institute AND Merck:**

Kirby Institute: [contact].

Merck Worldwide Product Safety: [contact]

7.4 Suspected Unexpected Serious Adverse Reaction (SUSAR)

The Project Team in collaboration with the Medical Officer will review and identify all serious events which fit the criteria of a SUSAR and requiring expedited reporting to relevant parties.

The definition of a SUSAR is a serious adverse event which is both suspected as being related to the drug (i.e. has a reasonable suspected causal relationship) and is unexpected) whereby the nature and severity is not consistent with known information (e.g. the Investigator's Brochure).

The sponsor must expedite the reporting of all SUSARs to all concerned investigators/institutions, IRB/IEC/s, and regulatory authorities within the reporting timeframe. Reports must comply with the applicable regulatory requirements and ICH Guideline for Clinical Safety Data Management: Definitions and Standards for Expedited Reporting.

Researchers must inform the IRB/IEC and regulatory authorities of all SUSARs that occur during the study that may affect the conduct of the study or the safety of the participants or their willingness to continue participation in the study. Researchers must inform the IRB/IEC as soon as possible of any new information from other published or unpublished studies which may have an impact on the continued ethical acceptability of the study or which may indicate the need for amendments to the study protocol.

All SAEs and SUSARs will be reported to the approving Human Research Ethics Committee as per local policy.

Coding

Serious Adverse Events will be assigned preferred terms and categorised into system organ classes according to the Medical Dictionary for Drug Regulatory Affairs (MedDRA) classification of the WHO terminology.

8. Packaging, labeling, storage and accountability of clinical trial supplies

All study drugs will be supplied via PBS following PBAC listing. The drugs should be dispensed under the supervision of the investigator or a qualified member of the investigational staff, or by a hospital/clinic pharmacist.

Medications must be stored, and dispensed according to PBS regulations as per standard practice.

8.1 Formulation

The elbasvir/grazoprevir (50mg/100mg) tablets are beige, oval-shaped, film-coated, debossed with “770” on one side and plain on the other. In addition to the active ingredients the tablets also contain the following inactive ingredients: colloidal silicon dioxide, copovidone, croscarmellose sodium, hypromellose, lactose monohydrate, magnesium stearate, mannitol, microcrystalline cellulose, sodium chloride, sodium lauryl sulfate, and vitamin E polyethylene glycol succinate.

8.2 Packaging and Labelling

The tablets are packaged into a carton (NDC 0006-3074-02) containing two (2) 14-count child-resistant dose packs for a total of 28 tablets.

8.3 Storage and handling

Elbasvir/grazoprevir packs should be stored in the original packs at controlled room temperature until required for administration. Elbasvir/grazoprevir should be stored at 20°C to 25°C (68°F to 77°F); excursions are permitted between 15°C and 30°C (59°F to 86°F).

Subjects should be counselled to store elbasvir/grazoprevir blister packs at room temperature not in the refrigerator.

All drug products should be stored in a securely locked area, assessable only to authorized site personnel. To ensure the stability of the study drug and to ensure proper product identification, the drug product should not be stored in a container other than the container in which they are supplied.

9. Biological samples

9.1 Laboratory supplies and sample processing

Laboratory supplies for collection of research specimens (plasma and whole blood) will be supplied by the Kirby Institute.

The following blood samples will be collected as time point specified in the schedule of assessments:

1. 10 mL EDTA plasma for HCV RNA testing and future HCV related research (20 mL will be collected at Screening and Baseline visits);
2. 4mL whole blood for human genomic DNA analysis collected at the screening and baseline visits only.

Samples will be collected by sites and then processed and stored at -70°C at the site local laboratory for bulk shipment to the Kirby Institute laboratory. Detailed sample processing instructions will be provided in the laboratory manual.

EDTA plasma samples will be used for study endpoint analysis. HCV viral load will be measured using in-house and commercial assays. Sequencing of the viral genome will also be performed as a more accurate means of genotyping. Data generated from the sequencing may also be used to distinguish relapse from reinfection and to examine the prevalence of mixed infection.

HCV sequencing/resistance testing

Sanger sequencing will be performed on a pre-treatment sample on all participants. Complementary RNA will be generated using SuperScript® VILO™ cDNA Synthesis Kit (Life Technologies, Carlsbad, CA) with random hexamers. Sequencing of NS5A will be performed on all participants. A fragment of the HCV genome covering Core, Envelope-1, hypervariable region-1 and beginning of Envelope-2 (E2) will be amplified using a method previously described. Sequencing of NS3/4, NS5A, NS5B, and full-length next generation sequencing may also be performed. Purified amplicons will be sequenced using the Sanger method and sequence chromatograms processed using RECall: a fully automated sequence analysis pipeline. Subtypes will be determined using the Oxford HCV Automated Subtype Tool. Reverse transcription, PCR and sequencing reaction and thermal cycling conditions will be performed as previously described. Further, Sanger sequencing and next generation sequencing will be performed among samples with persistent infection at risk of HCV mixed infection (e.g. treatment non-response). Lastly, Sanger sequencing and next generation sequencing will be performed among samples with HCV recurrence to distinguish HCV reinfection from viral relapse (detectable HCV RNA following HCV virological suppression).

HCV RNA point of Care testing (sub-study sites only)

Point of care testing for HCV RNA detection will be performed at each visit at selected sub study sites using the Xpert® HCV Viral Load assay for samples collected by finger-stick capillary whole-blood as described below. This point of care testing will be undertaken in addition to the standard of care (local laboratory).

The capillary whole-blood sample is collected from participants via a finger-stick [MiniCollect® Safety Lancet (Order Number 450429), Greiner Bio-One, Monroe, Frickenhausen, Germany] using procedures recommended by the World Health Organization³¹ and collected into a 100µL minivette collection tube [Minivette® POCT 100µl (Order number 17.2111.100), Sarstedt, Nümbrecht, Germany].

9.2 Shipping of biological samples

Samples must only be shipped to the Kirby Institute laboratory on the instruction from the Study Coordinator.

It is the responsibility of each site Principal Investigator to ensure that all site staff handling, packaging, and/or shipping biological samples understand and comply with International Air Transport Association (IATA) regulations relating to the handling and shipping of hazardous goods and/or diagnostic specimens.

9.3 Future use of biological samples

After the samples have been analysed for the study endpoints as specified in the protocol, remaining samples will be stored for use in future Human Research Ethics Committee approved hepatitis C related research. Additional consent will not be sought for this storage and future use. It is not optional. Subjects not wishing to have their samples stored or used in future hepatitis C related research will not be eligible to participate in this study.

10. Statistics

The statistical team and investigators at the Kirby Institute will be responsible for analysing the study data.

Primary Objective: To evaluate the proportion of patients with undetectable HCV RNA at 12 weeks post end of treatment (SVR12) following elbasvir/grazoprevir therapy among PWID with recent injecting drug use or receiving OST and chronic HCV genotype 1 or 4 infection and evaluate demographic and clinical predictors of non-response.

Hypothesis: *Elbasvir/grazoprevir therapy will lead to SVR12 >90% among PWID with recent injecting drug use or receiving OST and chronic HCV genotype 1 or 4 infection.*

Outcome: The primary endpoint for this aim is the proportion of participants with a treatment response (measured by SVR, undetectable HCV RNA 12 weeks after the completion of therapy).

Statistical analysis: The proportion of people with a response to HCV therapy will be evaluated. Factors associated with treatment response (as measured by SVR) will be assessed by univariate and multivariate logistic regression analyses. Factors hypothesized to be associated with HCV treatment response will be assessed including: sociodemographic factors (housing and education), injecting behaviours (recent injecting drug use prior to and during therapy and type of drug injected), and clinical factors (opioid substitution treatment, HCV genotype, fibrosis stage).

Sample Size: Assuming an overall SVR of 90% (135 of 150), the 95% confidence interval around this estimate will be 84.0% to 94.3%. This study will have robust power to examine the effect of treatment setting on SVR: e.g. 80% power to detect an odds ratio of 0.39 or 2.59 or more extreme (with alpha=0.05) for a variable that is 50% prevalent.

Secondary Objective: Estimate incidence and predictors of HCV reinfection after successful elbasvir/grazoprevir.

Hypothesis 2.1: The incidence of HCV reinfection following successful elbasvir/grazoprevir therapy will be <8 per 100 p-yrs among people with recent injecting drug use or receiving OST.

Hypothesis 2.2: HCV reinfection will be associated with ongoing \geq daily injecting drug use, and needle and syringe borrowing. OST and high-coverage access to needle and syringes will be associated with reduced HCV reinfection.

Outcome: Incidence of HCV reinfection following successful elbasvir/grazoprevir therapy.

Statistical analysis: Rates of HCV reinfection will be calculated using person-time of observation. The estimated date of reinfection will be calculated as the midpoint between the dates of the last undetectable HCV RNA test and the first detectable HCV RNA test at the time of HCV reinfection. Time at risk will commence at the date of undetectable HCV RNA at end of treatment and end at the first of estimated date of re-infection, death, loss-to-follow up or end of study. Confidence intervals for rates will be calculated using a Poisson distribution.

Cox proportional hazards analyses (or other appropriate regression models) will be used to estimate crude and adjusted hazard ratios and corresponding 95%CI to evaluate factors associated with reinfection. Factors hypothesised to be associated with reinfection include demographic factors (age, sex), injecting behaviours (current injecting drug use, daily injecting, type of drug injected, injecting equipment borrowing), use of needle and syringe programs, and opioid substitution treatment with time-updated co-variables.

Sample Size: Overall, based on previous reports of HCV reinfection among current PWID³², and assuming loss to follow-up is 20% per year, it is estimated that the overall reinfection rate will be 8/100 p-yrs (95%CI 5.3, 11.4; 337 p-yrs of follow-up; 27 reinfections). Overall (135 with successful therapy, 27 reinfections), we will have 80% power to detect a hazards ratio (HR) of 2.94 or greater (with alpha=0.05) for a variable 50% prevalent (e.g. ongoing injecting drug use).

Collateral research

Evaluation of HCV phylogenetics

All participants enrolled in this study with available plasma samples at screening or baseline (HCV RNA detectable) will be sequenced for HCV RNA for evaluation of HCV phylogenetics.

Evaluation of HCV re-infection

All participants with an ETR will be followed for up to three years post-ETR to assess HCV reinfection. Participants with viral recurrence (detectable HCV RNA following HCV virological suppression, reinfection rate: 8/100 person years, estimated n=27 x 2 samples=54 total samples) will be identified and available follow-up plasma samples assessed for re-infection.

The sensitivity and specificity of the Xpert® HCV Viral Load point-of-care test for detection of HCV RNA in plasma samples collected via venepuncture and capillary whole-blood samples collected by finger-stick will be assessed using both detectable and quantifiable thresholds (limit of quantification >10 IU/mL) for each assay compared to the local laboratory HCV RNA assay in plasma as the gold standard. A Bland-Altman difference plot will be generated to assess bias and agreement measurements, including limits of agreement, between the quantification of HCV by Xpert® HCV Viral Load both sample types, compared to the local laboratory HCV RNA assay in plasma.

11. Data Safety and Monitoring Board (DSMB).

A Data Safety Monitoring Board will not be used for this study as the drug is being prescribed and supplied according to indication via the PBS.

The study Medical Monitor, A/[name] will oversee all serious adverse events for DARLO-C. A/[name] is independent of the study project management team and Protocol Steering Committee. A/[name] is also a clinician at St Vincent's Hospital which is one of the recruiting sites. Should an SAE occur in a patient under A/[name] care the project team will seek an independent review of the SAE from a suitably qualified independent Infectious Diseases Specialist or Hepatologist.

12. Data collection, source documents and record retention

The Principal Investigator and the institution where the study will be conducted will permit study-related monitoring, audits, ethics committee review and regulatory inspection providing direct access to source documents.

Data will be collected on study specific electronic or paper copy case record forms. The Principal Investigator is responsible for ensuring the data collected are complete, accurate and recorded in a timely manner.

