32. Aspinall, E.J. et al. Treatment of hepatitis C virus infection among people who are actively injecting drugs: a systematic review and meta-analysis. *Clin Infect Dis* **57 Suppl 2**, S80-9 (2013).

19. Abbreviations List

ALT	Alanine Aminotransferase
AST	Aspartate Aminotransferase
DAA	Direct Acting Antiviral
End of treatment	Date of last dose of treatment
ETR	End of Treatment Response, undetectable HCV RNA at the completion of treatment
FBC	Full Blood Count (haemoglobin, WCC including differentials, platelets)
HCV	Hepatitis C Virus
IDUs	Injection Drug Users
IEC	Institutional Ethics Committee (Human Research Ethics Committee)
INR	International Normalized Ratio
IRB	Institutional Review Board (Human Research Ethics Committee)
LFTs	Liver Function Tests – albumin, ALT, AST, alkaline phosphatase, GGT, total bilirubin, total protein
LLOQ	Lower Limit Of Quantification
GGT	Gamma Glutamic Transpeptidase
Hgb	Haemoglobin
OST	Opioid Substitution Therapy
PEG-IFN	Pegylated interferon alfa 2a
PWID	People Who Inject Drugs
POC	Point of Care
RAS	Resistant Associated Substitutions
Reinfection	Detection of infection with an HCV strain which was distinct from the primary infecting strain among participants with either spontaneous or treatment-induced HCV virological suppression (≤ 15 IU/ml on Roche TaqMan).
SVR12	Sustained Virological Response, HCV RNA undetectable 12 weeks post-treatment
SVR24	Sustained Virological Response, HCV RNA undetectable 24 weeks post-treatment
Undetectable HCV RNA	HCV RNA results that are < 15 IU/ml (non-quantifiable), but “detectable” will be considered as undetectable HCV RNA
WCC	White Cell Count

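### As SVR12 is defined, a reinfection before Week 24 enters the predictors-of-non-response model as a drug failure; add a supplementary virological-failure analysis using the sequencing already planned

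*Combined protocol and SAP*

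**What the plan says.** Section 10 (Primary Objective, Outcome) defines treatment response by SVR, that is, "undetectable HCV RNA 12 weeks after the completion of therapy". The abbreviations list in Section 19 gives the same definition: "Sustained Virological Response, HCV RNA undetectable 12 weeks post-treatment". Neither has a clause for a new strain. The predictor analysis is built on this variable: "Factors associated with treatment response (as measured by SVR) will be assessed by univariate and multivariate logistic regression analyses". Its candidate factors include "injecting behaviours (recent injecting drug use prior to and during therapy and type of drug injected", with opioid substitution treatment among the clinical factors.

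For the secondary objective, Section 10 says: "Time at risk will commence at the date of undetectable HCV RNA at end of treatment". The factors for reinfection include "injecting behaviours (current injecting drug use, daily injecting, type of drug injected, injecting equipment borrowing", again with opioid substitution treatment, as time-updated covariates.

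Section 9.1 plans pre-treatment sequencing for all participants, and Sanger and next-generation sequencing of recurrences "to distinguish HCV reinfection from viral relapse". Section 6.1 repeats that suspected relapse or reinfection will be sequenced and says no extra sample is needed. Nothing links the sequencing result to the SVR12 variable or to its predictor model.

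**The concern.** The plan itself treats the 12 weeks between end of treatment and the SVR12 visit as time in which reinfection can occur. A person reinfected in that window and still viraemic at Week 24 meets the definition of non-response, although the drug worked. The midpoint rule would also date that event about Week 18 in the reinfection analysis, so one event can serve both as a failure of therapy and as a reinfection after successful therapy.

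This matters mainly for the predictor model. Predictors of non-response are part of the primary objective, and Section 1 motivates the trial by the limited data on recent injectors. Whether injecting weakens response to the drug, or only exposes people to a new infection, are different questions. Hypothesis 2.2 expects frequent injecting and syringe borrowing to raise reinfection and opioid substitution treatment to lower it. A model that mixes the two outcomes would therefore shift the apparent effect of these factors on drug response in a known direction.

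**Working it through.** **Inputs from Section 10.** 150 participants; assumed SVR12 of 135/150, hence 15 non-responders; reinfection rate 8/100 person-years (5.3 to 11.4), from 27 events in 337 person-years; detectable hazard ratio 2.94 for a 50% prevalent exposure. The window is 12 weeks = 84 days = 84/365.25 = 0.230 years.

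**The plan's own figures.**
- The exact (Clopper-Pearson) 95% interval for 135/150 is 84.0% to 94.3%, as stated.
- 27/337 = 8.01 per 100 person-years. The exact Poisson interval is 5.3 to 11.7. The stated upper limit of 11.4 is slightly lower; I use the stated limits below.
- 27 events give 80% power for a hazard ratio of 2.94 by Schoenfeld's formula, as stated.

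**Expected reinfections before Week 24.** Expected number = n × (1 − exp(−rate × 0.230)). The number at risk lies between 135 (the assumed responders) and 150 (everyone).

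| Rate per 100 p-yrs | n = 135 | n = 150 | Share of 15 non-responders |
|---|---|---|---|
| 5.3 | 1.6 | 1.8 | 11-12% |
| 8 | 2.5 | 2.7 | 16-18% |
| 11.4 | 3.5 | 3.9 | 23-26% |

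The chance of at least one such event, 1 − exp(−expected number), runs from about 80% to 98%. The counts ignore loss to follow-up within the 12 weeks and assume that each reinfection is still detectable at Week 24.

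**Effect on the proportion.** If 2 or 3 of the 15 assumed non-responders are reinfections:
- counted as virological responders: 137/150 = 91.3% (85.6 to 95.3) or 138/150 = 92.0% (86.4 to 95.8);
- excluded: 135/148 = 91.2% (85.4 to 95.2) or 135/147 = 91.8% (86.2 to 95.7).

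**Effect on the predictor model.** Take a 50% prevalent exposure with no effect on true failure and a hazard ratio of 2.94 for reinfection, at 8/100 overall.
- Unexposed rate = 2 × 8/(1 + 2.94) = 4.06; exposed rate = 2.94 × 4.06 = 11.94 per 100 person-years.
- True failure = 12.5/150 = 8.33% in both groups (15 less 2.5 reinfections).
- Observed non-response = 0.0833 + 0.9167 × (1 − exp(−rate × 0.230)), which is 9.19% unexposed and 10.82% exposed.
- Odds ratio = (0.1082/0.8918)/(0.0919/0.9081) = 1.20.

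With true failure at 10% it is 1.17. Over 5.3 to 11.4 per 100 person-years and both failure rates it runs from 1.11 to 1.27. The correct value is 1.0.

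**Set against sampling error.** With 15 events split evenly over two groups of 75, the standard error of the log odds ratio is √[2 × (1/7.5 + 1/67.5)] = 0.54. The bias, ln 1.20 = 0.18, is about a third of that.

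**The case against.** Counting all viraemia as failure is a legitimate definition. The objectives name SVR12 itself, and the trial seeks real-world responses. One event contributing to two endpoints is not in itself an error. This stands, and it is why the primary endpoint and its model should not change.

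The exposures also differ in timing. The SVR model uses injecting before and during therapy; reinfection before Week 24 depends on injecting after therapy. The odds ratio of 1.2 assumes that the first fully predicts the second, so the true bias would be smaller. The reinfection rate may be high for this cohort too: the plan takes it from reports on current injectors, while eligibility also admits people through opioid substitution treatment alone, and Hypothesis 2.1 expects less than 8. Both points stand and reduce the size.

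Three stronger readings are tempting, and the documents do not support them.
- A reader might infer that the plan expressly classifies early reinfections as drug failures. It does not say so; this follows from the definition and the lack of an exception.
- A reader might infer a large spurious effect of injecting. Rates of 15 versus 1 per 100 person-years with 8% true failure would give an odds ratio of 1.4, but those rates appear nowhere in the plan. Its own hazard ratio gives about 1.2.
- A reader might infer that reinfection pulls SVR12 below a 90% success criterion. The plan states a hypothesis above 90% but no test or decision rule, and does not say whether its assumed 90% is before or after reinfections.

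Finally, sequencing may not resolve every recurrence. The documents give no success rate. That is a reason to state a rule for unresolved cases.

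**Conclusion.** The point holds as a modest weakness of the predictor analysis, not as an error in the primary endpoint. Followed as written, the plan would place about 2.5 to 2.7 reinfections (1.6 to 3.9) among some 15 non-responses. That could produce an odds ratio near 1.2 (1.1 to 1.3) for an exposure that affects only reinfection.

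This rests on the plan's reinfection rate applying evenly over the first 12 weeks, on viraemia persisting to Week 24, on the plan's hazard ratio of 2.94 as an illustration, and on full overlap between injecting before or during therapy and injecting afterwards. Partial overlap makes it smaller.

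The bias is small beside the sampling error, but its direction is predictable, it touches a stated part of the primary objective, and the data needed to deal with it are already to be collected. Correcting it is a cheap improvement.

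**What to change.** Keep SVR12, with all viraemia counted as failure, as the primary endpoint, and keep its predictor model. Add to Section 10 a supplementary proportion and predictor model for virological failure, with these rules fixed before the data are seen:

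- sequence-confirmed reinfections by Week 24 are excluded from the analysis set;
- a sensitivity analysis counts them as virological responders instead;
- recurrences that sequencing cannot resolve stay in as failures.

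The same paragraph should say whether an early reinfection also counts in the reinfection analysis. The text there starts the clock at end of treatment and follows everyone with an end-of-treatment response, yet bases its power on 135 participants with successful therapy.

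The cost is a few sentences of analysis text; no new visit, sample or assay is needed. The downside is two or three fewer events in a supplementary model that is already sparse, and dependence on a sequencing success rate that the documents do not give. The number of unresolved recurrences should therefore be reported.
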